**Table 6. Time Point Response Criteria (non-target disease only)**

Non-Target Lesions	New Lesions	Overall Response
CR	No	CR
Non-CR/non-PD	No	Non-CR/non-PD 
Not all evaluated	No	NE
Unequivocal PD	Yes or No	PD
Any	Yes	PD

 Non-CR/non-PD is preferred over SD for non-target disease since SD is used as endpoint for assessment of efficacy in trials so to assign this category when no lesions can be measured is not advised.

The best overall response is the best response recorded from the start of study treatment until the end of treatment taking into account any requirement for confirmation. In general, the subject's best response assignment will depend on the achievement of both measurement and confirmation criteria and will be determined by combining the subject's status of target lesions, non-target lesions, and new lesions.

- **Residual Disease:** Any measurable tumor that was considered a target or non-target or new lesion  $\geq 1$  cm.
- **Symptomatic Deterioration:** Subjects with global deterioration of health status requiring discontinuation of treatment without objective evidence of disease progression at that time, and not related to study treatment or other medical conditions should be reported as progressive disease due to "symptomatic deterioration." Every effort should be made to document objective progression even after discontinuation of treatment due to symptomatic deterioration. Symptomatic deterioration that may lead to discontinuation of treatment include, but is not limited to, symptoms such as:
  - Weight loss  $> 10\%$  of body weight.

- Worsening of disease-related symptoms (e.g., worsening dyspnea, increasing pain/increasing requirement for narcotic analgesics).
- Decline in performance status of > 1 level on ECOG scale.

### 8.5 Confirmation Measurement

Response will be confirmed within 6 weeks.

### 8.6 Guidelines for Evaluation of Measurable Disease

All measurements should be taken and recorded in metric notation using a ruler or calipers. All baseline evaluations should be performed as closely as possible to the beginning of treatment and never more than 4 weeks before the beginning of the treatment.

The same method of assessment and the same technique should be used to characterize each identified and reported lesion at baseline and during follow-up. Imaging-based evaluation is preferred to evaluation by clinical examination unless the lesion(s) being followed cannot be imaged but are assessable by clinical exam.

- **Clinical Lesions:** Clinical lesions will only be considered measurable when they are superficial (e.g., skin nodules and palpable lymph nodes) and  $\geq 10$  mm diameter as assessed using calipers (e.g., skin nodules). In the case of skin lesions, documentation by color photography, including a ruler to estimate the size of the lesion, is recommended.
- **Chest x-ray:** Lesions on chest x-ray are acceptable as measurable lesions when they are clearly defined and surrounded by aerated lung. However, CT is preferable.
- **Conventional CT and MRI:** This guideline has defined measurability of lesions on CT scan based on the assumption that CT slice thickness is 5 mm or less. If CT scans have slice thickness greater than 5 mm, the minimum size for a measurable lesion should be twice the slice thickness. MRI is also acceptable in certain situations (e.g., for body scans).

Use of MRI remains a complex issue. MRI has excellent contrast, spatial, and temporal resolution; however, there are many image acquisition variables involved in MRI, which greatly impact image quality, lesion conspicuity, and measurement. Furthermore, the availability of MRI is variable globally. As with CT, if an MRI is performed, the technical specifications of the scanning sequences used should be optimized for the evaluation of the type and site of disease. Furthermore, as with CT, the modality used at follow-up should be the same as was used at baseline and the lesions should be measured/assessed on the same pulse sequence. It is beyond the scope of the RECIST guidelines to prescribe specific MRI pulse sequence parameters for all scanners, body parts, and diseases. Ideally, the same type of scanner should be used and the image acquisition protocol should be followed as closely as possible to prior scans. Body scans should be performed with breath-hold scanning techniques, if possible.

- **PET-CT:** At present, the low dose or attenuation correction CT portion of a combined PET-CT is not always of optimal diagnostic CT quality for use with RECIST measurements. However, if the site can document that the CT performed as part of a PET-CT is of identical diagnostic quality to a diagnostic CT (with IV and oral contrast), then the CT portion of the

PET-CT can be used for RECIST measurements and can be used interchangeably with conventional CT in accurately measuring cancer lesions over time. Note, however, that the PET portion of the CT introduces additional data which may bias an investigator if it is not routinely or serially performed.

- **Ultrasound:** Ultrasound is not useful in assessment of lesion size and should not be used as a method of measurement. Ultrasound examinations cannot be reproduced in their entirety for independent review at a later date and, because they are operator dependent, it cannot be guaranteed that the same technique and measurements will be taken from one assessment to the next. If new lesions are identified by ultrasound in the course of the study, confirmation by CT or MRI is advised. If there is concern about radiation exposure at CT, MRI may be used instead of CT in selected instances.
- **Endoscopy, Laparoscopy:** The utilization of these techniques for objective tumor evaluation is not advised. However, such techniques may be useful to confirm complete pathological response when biopsies are obtained or to determine relapse in trials where recurrence following complete response (CR) or surgical resection is an endpoint.
- **Tumor Markers:** Tumor markers alone cannot be used to assess response. If markers are initially above the upper normal limit, they must normalize for a subject to be considered in complete clinical response.
- **Cytology, Histology:** These techniques can be used to differentiate between partial responses (PR) and complete responses (CR) in rare cases (e.g., residual lesions in tumor types, such as germ cell tumors, where known residual benign tumors can remain).

The cytological confirmation of the neoplastic origin of any effusion that appears or worsens during treatment when the measurable tumor has met criteria for response or stable disease is mandatory to differentiate between response or stable disease (an effusion may be a side effect of the treatment) and progressive disease.

- **FDG-PET:** While FDG-PET response assessments need additional study, it is sometimes reasonable to incorporate the use of FDG-PET scanning to complement CT scanning in assessment of progression (particularly possible 'new' disease). New lesions on the basis of FDG PET imaging can be identified according to the following algorithm:
- Negative FDG-PET at baseline, with a positive FDG-PET at follow-up is a sign of PD based on a new lesion.
- No FDG-PET at baseline and a positive FDG-PET at follow-up: If the positive FDG-PET at follow-up corresponds to a new site of disease confirmed by CT, this is PD. If the positive FDG-PET at follow-up is not confirmed as a new site of disease on CT, additional follow-up CT scans are needed to determine if there is truly progression occurring at that site (if so, the date of PD will be the date of the initial abnormal FDG-PET scan). If the positive FDG-PET at follow-up corresponds to a pre-existing site of disease on CT that is not progressing on the basis of the anatomic images, this is not PD.
- FDG-PET may be used to upgrade a response to a CR in a manner similar to a biopsy in cases where a residual radiographic abnormality is thought to represent fibrosis or scarring.

The use of FDG-PET in this circumstance should be prospectively described in the protocol and supported by disease-specific medical literature for the indication. However, it must be acknowledged that both approaches may lead to false positive CR due to limitations of FDG-PET and biopsy resolution/sensitivity.

Note: A ‘positive’ FDG-PET scan lesion means one which is FDG avid with an uptake greater than twice that of the surrounding tissue on the attenuation corrected image.

## **9 SAFETY EVALUATION**

### **9.1 Adverse Events**

#### **9.1.1 Definition**

An adverse event or adverse experience (AE) is any untoward medical occurrence associated with the use of a drug in humans, whether or not considered drug related. Therefore, an AE can be **ANY** unfavorable and unintended sign (including an abnormal laboratory finding), symptom, or disease temporally associated with the use of a medicinal (investigational) product, whether or not considered related to the medicinal (investigational) product (attribution of ‘unrelated’, ‘unlikely’, ‘possible’, ‘probable’, or ‘definite’).

An AE is considered “unexpected” if it is not listed in the investigator brochure or is not listed at the specificity or severity that has been observed; or if an investigator brochure is not required or available, is not consistent with the risk information described in the general investigational plan in other study-related documents.

##### **9.1.1.1 Diagnosis Versus Signs and Symptoms**

If known, a diagnosis should be recorded on the CRF rather than individual signs and symptoms (e.g., record only liver failure or hepatitis rather than jaundice, asterixis, and elevated transaminases). However, if a constellation of signs and/or symptoms cannot be clinically characterized as a single diagnosis or syndrome at the time of reporting, each individual event should be recorded as an AE or SAE on the CRF. If a diagnosis is subsequently established, it should be reported as follow-up information.

##### **9.1.1.2 Adverse Events Occurring Secondary to Other Events**

In general, AEs occurring secondary to other events (e.g., cascade events or clinical sequelae) should be identified by their primary cause. For example, if severe diarrhea is known to have resulted in dehydration, it is sufficient to record only diarrhea as an AE or SAE on the CRF.

However, clinically significant AEs occurring secondary to an initiating event that are separated in time should be recorded as independent events on the CRF. For example, if a severe gastrointestinal hemorrhage leads to renal failure, both events should be recorded separately on the CRF.

### 9.1.1.3 Abnormal Laboratory Values

Only clinically significant laboratory abnormalities that require active management will be recorded as AEs or SAEs on the CRF (e.g., abnormalities that require study drug dose modification, discontinuation of study treatment, more frequent follow-up assessments, further diagnostic investigation, etc.).

If the clinically significant laboratory abnormality is a sign of a disease or syndrome (e.g., alkaline phosphatase and bilirubin 5 x the upper limit of normal associated with cholecystitis), only the diagnosis (e.g., cholecystitis) needs to be recorded on the Adverse Event CRF.

If the clinically significant laboratory abnormality is not a sign of a disease or syndrome, the abnormality itself should be recorded as an AE or SAE on the CRF. If the laboratory abnormality can be characterized by a precise clinical term, the clinical term should be recorded as the AE or SAE. For example, an elevated serum potassium level of 7 mEq/L should be recorded as “hyperkalemia”

Observations of the same clinically significant laboratory abnormality from visit to visit should not be repeatedly recorded as AEs or SAEs on the CRF, unless their severity, seriousness, or etiology changes.

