	
Alpha-Fetoprotein (AFP)
 
HBsAg; HCV Ab; (if unknown)
 
Viral Load (if either or both HBsAg or HCV Ab are positive)
 
PK/PD sVEGF-2 Sampling
 
Immune Biomarker Sampling
 
ECOG Performance Status
 
Electrocardiogram
 
CT Scan (within 4 weeks)
 
Adverse Events

Statistical Analysis
	
Sample Size Determination: Sample size for the Phase 1 portion depends on the unknown dose-toxicity profile. For the Phase 2 portion, with <math>\alpha = 0.05</math>, assessment of 37 patients gives 80% power to detect minimum 20 percentage point improvement in the 24 week PFS response rate, assuming a 50% rate under the standard of care.
 
Randomization: No randomization is required.
 
Efficacy Analysis: Primary interest is in the PFS response rate 24 weeks after enrollment. The response rate will be described by binomial proportion estimates and 95% confidence intervals. All enrolled patients will be included in this primary analysis.
 
Safety Analysis: Adverse events will be tabulated. AE rates will be described using binomial proportions and 95% confidence intervals.

**Subject Name: (Network Sites use Initials)** \_\_\_\_\_

**Medical Record No.: (Network Sites use Subject ID#)** \_\_\_\_\_

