### 3.3.3 Treatment Cycle

A cycle will be defined as 28 days. At the full dose, this will be 21 days on treatment with 7 days off. However, in the case of a dose reduction patients will be treated starting on day 1 of the cycle, every other day for 10 doses. Treatment will continue until progression or toxicity. Response/ progression will be assessed Q 8 weeks or q 2 months by CT scan. (MRI when patients have contraindication to CT). Steady state PK will be assessed at Day 15, as this is the first study in patients with liver dysfunction.

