## 6.2 Dose Modifications

### 6.2.1 Definition of Dose-Limiting Toxicity

A DLT is any Grade 3 or higher toxicity that is possible, probable, or definitely related to study drug.

Management and dose modifications associated with the above AEs are outlined in the below sections. Dose level will be, considered tolerable following completion of 1st cycle of treatment.

Patients who experience a DLT will be dose reduced to the next lower dose cohort for continuation on the study.

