#### **11.7 Safety Analysis**

The safety sample will include all patients exposed to the study drug.

Toxicity frequency will be tabulated by grade across all dose levels and cycles for all patients in the safety sample, and for the subset treated at the recommended Phase 2 dose. These tables will be produced at 3 time points:

1. At the end of the Phase 1b study.
2. At the Phase 2 interim analysis.
3. At the Phase 2 final analysis.

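### The AE recording rule lets unmanaged laboratory abnormalities drop out of the by-grade toxicity tables, and no analysis grades the collected laboratory values directly

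*Combined protocol and SAP*

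**What the plan says.** Recording. The AE definition in Section 9.1.1 covers any unfavorable sign, "including an abnormal laboratory finding", and sets no management condition. Section 9.1.1.3 then narrows this for laboratory tests: "Only clinically significant laboratory abnormalities that require active management will be recorded as AEs or SAEs on the CRF". Its examples of active management are "abnormalities that require study drug dose modification, discontinuation of study treatment, more frequent follow-up assessments, further diagnostic investigation, etc". Where a diagnosis is known, Section 9.1.1.1 has the site enter the diagnosis in place of its components: "record only liver failure or hepatitis rather than jaundice, asterixis, and elevated transaminases".

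Reporting. Table 7 (Phase 1) marks Grades 1-4 at every attribution. Table 8 (Phase 2) marks Grades 1-2 when attribution is possible, probable or definite, and Grades 3-4 at every attribution.

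Analysis. Section 11.7: "Toxicity frequency will be tabulated by grade across all dose levels and cycles for all patients in the safety sample", and again for the subset at the recommended Phase 2 dose, at the end of Phase 1b, the Phase 2 interim and the Phase 2 final analysis. It does not say whether grades come from AE forms or from laboratory values. The synopsis adds: "AE rates will be described using binomial proportions and 95% confidence intervals".

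Collection. Sections 7.1 to 7.5 and 7.7 and Table 4 schedule a full blood count, AST, ALT, bilirubin, alkaline phosphatase, creatinine and albumin at baseline, Cycle 1 Day 1, Cycle 1 Day 15, Day 1 of every later cycle and end of treatment. The 1-year visit (Section 7.6) has only an immune sample.

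**The concern.** Safety in HCC is the first secondary objective (Section 3.2). Entry requires Child-Pugh A but allows AST up to 5 x ULN, bilirubin up to 3 mg/dL and platelets down to 60,000/mm³ (Section 4.1), and Section 1.6.1 describes limited liver reserve. Section 3.3.3 justifies Day 15 PK sampling "as this is the first study in patients with liver dysfunction". That remark is about PK and not AE capture, but it shows that hepatic tolerability is a real question here. Section 4.1 also says that the relaxed neutrophil and platelet cut-offs are thought to be safe, and no planned summary of the counts would test this.

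If the graded tables come from AE forms, a laboratory abnormality appears only after a site has judged it clinically significant and in need of management. The rate then partly measures that judgment. The values that would settle the matter are already drawn, but no analysis in Sections 11.5 to 11.8 or 12 uses them for safety. At stake is the completeness of the laboratory toxicity profile.

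**Working it through.** The plan states no figure on this point, so there is none to reproduce. The check sets the recording rule against the dose rules, the reporting tables and the analysis sections.

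**Step 1. Which laboratory changes pass the Section 9.1.1.3 filter?**

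| Laboratory change | What other sections require | Passes the filter? |
|---|---|---|
| Drug-related Grade 3-4 | Dose interruption (Table 3, Section 6.2.3) and reduction (Section 6.2.4) | Yes: dose modification is listed as active management |
| Any grade that leads to closer follow-up or further tests | None needed | Yes: both are listed as active management |
| Grade 1-2, no action taken | Table 3 requires no interruption or reduction | No |
| Grade 3-4 judged unrelated or unlikely, no action taken | The dose rules apply to drug-related events only | No |

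The last row can arise because Section 9.1.2 attributes an event to unrelated or unlikely when the patient's clinical state explains it, and worsening liver tests in advanced HCC may be read that way.

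**Step 2. Is the DLT count exposed?** Section 6.2.1: "A DLT is any Grade 3 or higher toxicity that is possible, probable, or definitely related to study drug". There is no laboratory exception, and such events fall in the first row. The DLT count is therefore largely protected.

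**Step 3. Do Tables 7 and 8 close the gap?** They say which AEs are reported. Section 9.1.1.3 decides which laboratory values become AEs. If the filter acts first, the tables cannot restore what it removed. If Section 9.1.1 and the tables prevail, Section 9.1.1.3 contradicts them. No text says which governs.

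**Step 4. Is there a second route into the analysis?** Section 11.5 covers biomarkers and viral titers. Section 11.6 covers efficacy and correlative endpoints, with an exploratory look at toxicity by exposure quartile. Section 11.7 covers toxicity by grade, and Section 12 covers PK/PD and immune markers. None plans a worst-grade or shift table from chemistry or hematology.

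**Step 5. Size.** The planned Phase 2 sample, all at the recommended dose, is 6 + 31 = 37. One omitted patient lowers a rate by 1/37 = 2.7 percentage points. The documents give neither the true frequency of low-grade changes nor the fraction recorded. As an illustration only, assume that 15 of 37 patients have a given Grade 1-2 laboratory abnormality. With exact (Clopper-Pearson) 95% intervals:

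| Assumed fraction recorded | Patients tabulated | Rate | 95% CI |
|---|---|---|---|
| All | 15/37 | 40.5% | 24.8% to 57.9% |
| About 75% | 11/37 | 29.7% | 15.9% to 47.0% |
| About 50% | 7/37 | 18.9% | 8.0% to 35.2% |
| About 25% | 4/37 | 10.8% | 3.0% to 25.4% |

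The interval reflects sampling error only, so it does not warn the reader of incomplete recording.

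**The case against.** The best defence is that the rule is broad and the rest of the protocol leans towards recording. Active management includes closer follow-up and further diagnostics, so a liver-test rise that prompts a repeat draw is recordable. Drug-related Grade 3/4 events call for dose interruption or reduction and so qualify. Section 9.1.1.4 provides for recording a preexisting condition that worsens. Table 8 marks Grade 3-4 events even when unrelated. All of this stands, and it confines the point to the last two rows of the Step 1 table.

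A reader might infer that hepatic and blood-count toxicity as a whole is under-reported, or that severe drug-related toxicity and DLTs are missed. The documents do not support either inference, for the reasons in Steps 1 and 2. A reader might also infer that Section 9.1.1.1 removes hepatic events. It does not: the patient still has a recorded hepatic diagnosis, and where no single diagnosis fits, each sign is recorded separately. It can change only the term and grade under which the event is tabulated.

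That the tables rest on AE forms is also an inference. The synopsis wording makes it reasonable, but Section 11.7 names no source. Finally, laboratory-derived grades carry no attribution, so they complement the AE tables and do not replace them.

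**Conclusion.** Followed as written, the plan can under-count Grade 1-2 laboratory changes that need no action, and Grade 3-4 laboratory changes judged unrelated and left unmanaged. This rests on two assumptions: that the by-grade tables are built from AE forms, and that Section 9.1.1.3 is applied before Tables 7 and 8. The plan confirms neither, and that silence itself needs correcting.

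The direction is downward. The size cannot be computed from the documents, and the illustration shows only how a rate moves under assumed recording. Nothing supports a numerical claim about missing severe events. The Phase 2 decision rule, sample size and significance level use PFS response only and are unaffected. This is a cheap improvement to the safety analysis and does not undermine the trial.

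**What to change.** 1. In Section 11.7, name the data source for each toxicity table.
2. Add laboratory tables that derive CTCAE v4 grades directly from the chemistry and hematology collected at each treatment visit. For each gradable test, report the worst post-baseline grade and the baseline-to-worst shift, with exact 95% confidence intervals on the rates. The shift matters because patients may enter with abnormal values.
3. Produce these for all treated patients and for the recommended Phase 2 dose subset, at the three time points already planned, beside the attributed AE tables.
4. Reconcile the recording rule in Section 9.1.1.3 with the AE definition in Section 9.1.1 and with Tables 7 and 8, and state which governs laboratory findings.

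Cost: some programming, and laboratory data entry if the values are not already in the eCRF, which the documents do not make clear. No visit, sample, dose rule or sample size changes. Reported laboratory rates would be higher and would carry no attribution, so the table footnotes should say so.

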### 9.1.1.4 Preexisting Medical Conditions (Baseline Signs and Symptoms)

A preexisting medical condition should be recorded as an AE or SAE only if the frequency, severity, or character of the condition worsens during the study. When recording such events on an Adverse Event CRF, it is important to convey the concept that the preexisting condition has changed by including applicable descriptors (e.g., “more frequent headaches”).

